9.3 Variables

9.3.1 **Demographic Data**

The demographic data listed in Table 5 will be collected about subjects and readers. In addition, every effort will be made to collect these data from readers who decline to participate as well.

Table 5 **Demographic Data to Be Collected**

| Group | Demographic Factors | | |
|------------------|---|--|--|
| Subjects | • Age | | |
| | • Gender | | |
| | • Race | | |
| | Reason for scan | | |
| | • Country | | |
| | Imaging centre | | |
| | Type of medical practice of referring physician (primary, secondary, tertiary) | | |
| | VIZAMYL™ dose in MBq or mCi | | |
| | Type of anatomic images available, if any (MRI and/or CT) | | |
| Clinical readers | • Age | | |
| | • Gender | | |
| | • Race | | |
| | • Country | | |
| | • Institution | | |
| | VIZAMYL TM reading training status | | |
| | • VIZAMYL TM reading training method (electronic, in-person, or both) | | |
| | • Date(s) of VIZAMYL TM reading training (this will be used to determine the time from | | |
| | last training to the date of image interpretation) | | |
| | Training with other amyloid PET imaging agents | | |

[figure not shown]

Table 5 Demographic Data to Be Collected

| Group | Demographic Factors |
|-------|---|
| | Medical specialty |
| | Years of experience reading PET images |
| | Number of brain PET scans read in clinical practice |
| | Type of medical practice (primary, secondary, tertiary) |
| | • Prior experience (clinical or research) with any amyloid PET imaging agent (including |
| | VIZAMYL TM) |

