9.4 Data Sources

9.4.1 Strategies and Data Sources

Data from subjects and clinical readers can be obtained prospectively, or existing data can be used. Expert image reads will be obtained prospectively from expert readers who consent to participate. Data sources will be the images and patient medical records. Image interpretations and other data will be recorded directly onto eCRFs; images will be provided electronically. All measurements are considered standard for assessment of a diagnostic test.

Consenting eligible clinical readers (1 to 5 per country) will be selected and demographic information about them will be collected. They will each read VIZAMYLTM PET images obtained in clinical practice to generate the primary data that will be used to determine diagnostic accuracy.

Participating subjects will have been administered VIZAMYLTM intravenously and will have subsequently undergone PET brain imaging. Demographic information about the subject will be obtained from the imaging site where the subject is/was scanned. All VIZAMYLTM PET images (at least 200 images) and any associated anatomic images (brain CT and/or MRI) in this study will be acquired as part of clinical practice in Europe.

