The by-variable summaries will include estimates of diagnostic accuracy, sensitivity, specificity, PPV, and NPV along with 95% CIs for data pooled within each category. They will also show the number of clinical readers in each category and the number and percentage of clinical readers in each category with diagnostic accuracy <70%, >70% to $\le80\%$, >80% to $\le90\%$, and >90%.

The certainty of image classification will be summarised.

Safety Analyses

The number and percentage of subjects with 1 or more treatment-emergent AEs will be summarised. Additionally, treatment-emergent AEs will be coded and summarised by system organ class and preferred term. Treatment-emergent AE summaries will be provided by relationship to study drug and severity. Treatment-emergent serious AEs (SAEs) will also be summarised.

Interim Analysis

No formal interim analyses of the data are planned for this study. Interim progress reports of enrolment and safety will be provided annually.

Analyses of Study Limitations

Please see Section 9.9 below.

Evaluation of Impact of Study Results on Marketing Authorisation

The Sponsor will evaluate whether the study results have an impact on the marketing authorisation and will, if necessary, submit to the EMA an application to vary the marketing authorisation.

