3.3 Study treatments and assessments

Participating subjects will receive (or will have received) VIZAMYL™ intravenously prior to PET imaging, according to clinical practice.

Clinical readers may or may not have completed any training in reading VIZAMYL™ images, and some may have completed 1 or more VIZAMYL™ reader training programmes. They also may or may not have prior experience in reading VIZAMYL™ images.

Expert readers will have been trained in reading VIZAMYL™ images and will have experience in reading amyloid PET images.

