4.2 Secondary endpoints

- The numbers and percentages of images for which 5 expert readers agree, 4 expert readers agree, and 3 expert readers agree.
- Estimates of diagnostic accuracy, sensitivity, specificity, PPV, and NPV by the following variables:
 - Country
 - Time from training to image interpretation (<6 months, ≥ 6 months)
 - Specialty of the reader
 - Training method (s) used by the clinical reader (in-person, electronic, or both)
 - Number of scans read by the clinical reader in practice prior to the study (<50, ≥ 50)
 - Reader classification certainty (1 to 5)
- Safety Endpoint:- Adverse events (AEs)

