7 STATISTICAL CONSIDERATIONS AND ANALYSIS

7.1 Derived Variables

Not applicable

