8.4.2 Clinical Reader - demographic and baseline characteristics

Continuous demographic variable clinical reader's age will be summarised descriptively, and the following categorical demographic and baseline variables will be summarised using counts and percentages. Summaries will be based on the efficacy clinical reader population.

- Gender
- Race
- Country

Baseline characteristics:

- VIZAMYL™ reading training status
- Number of times training done (1, 2, ≥ 3)
- VIZAMYL™ reading training method (electronic, in-person, or both)
- Training with other amyloid PET imaging agents
- Medical specialty
- Time (month) from last training to the date of image interpretation (<6 months, ≥ 6 months)
- Number of brain PET scans read in clinical practice (<50, ≥ 50)
- Type of medical practice (primary, secondary, tertiary)
- Prior experience (clinical or research) with any amyloid PET imaging agent (including VIZAMYL™)

In addition, the following continuous baseline characteristics will be summarised descriptively:

- Duration (months) from last training to the date of image interpretation
- Years of experience reading PET images
- Number of brain PET scans read in clinical practice
- Years of experience reading PET images

- Number of times training done

Listings will be provided for each clinical reader's demographic and baseline characteristics.

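### Time since training and training method are not limited to training completed before the read; in addition, exactly 70% accuracy falls in no band, and the experience count has a loose as-of point for existing reads

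*SAP*

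**What the plan says.** Protocol 9.4.1 allows both data sources: "Data from subjects and clinical readers can be obtained prospectively, or existing data can be used". Training before reading is not required. SAP 3.3 states "Clinical readers may or may not have completed any training in reading" the product's images, and adds that some readers may have trained more than once.

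**Training.** Protocol Table 5 collects the training method and the training date or dates. It says of the dates that "this will be used to determine the time from" the most recent training to the read. SAP 8.4.2 carries the same definition, "Time (month) from last training to the date of image interpretation", cut at <6 and ≥6 months. The training-method subgroup (in-person, electronic, or both) has no date attached in protocol 9.7 or in SAP 4.2 and 8.6.3.

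**Bands.** Protocol 9.7 asks for the "number and percentage of clinical readers in each category with diagnostic accuracy <70%, >70% to" ≤80%, then >80% to ≤90%, then >90%. SAP 8.6.3 prints the same four bands.

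**Experience.** The subgroup in SAP 4.2, also in SAP 8.6.3 and protocol 9.7, is "Number of scans read by the clinical reader in practice prior to the study". The item collected in Table 5 is "Number of brain PET scans read in clinical practice", one count per reader without an as-of date. SAP 8.4.2 applies the 50-scan cut to that item directly.

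The SAP section headed "7.1 Derived Variables" is marked not applicable, so none of these variables has a derivation rule there.

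**The concern.** The secondary objective is to look for factors associated with interpretation errors, and it names training method and the gap between training and reading. With existing reads in the study, a reader may have trained after the read, either for the first time or again. The plan's definition attaches that later training to the earlier read, although it cannot have influenced it. The tables that answer the secondary objective would then mix reads made after training with reads made before it, under a label that says recently trained.

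The other two points are smaller. A reader at exactly 70% would be missing from the band table, so its percentages would not add to 100%. An early existing read could be filed under ≥50 scans because of scans read afterwards.

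**Working it through.** **Inputs.** The reader cap is 7.5% of images (protocol 9.2.5), and the protocol's own example reproduces: 0.075 × 200 = 15 images. Assumed accuracy is 90% (protocol 9.5, SAP 5). Cut-offs and bands are those of SAP 8.6.3. The plan gives no figure for how many reads predate training, so that number cannot be computed.

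**1. Training gap.** Gap = read date − date of last training.
- Only training 3 months after the read: gap = −3 months. Since −3 < 6, a literal rule gives <6 months.
- Last training 12 months after the read: gap = −12 months, again <6 months.
- Illustration with two courses, 8 months before and 1 month after the read: the gap to the training that preceded the read is 8 months (≥6), but last training gives −1 month (<6).

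**2. Training method.** A reader trained in person before the read and electronically after it is classed as both, although only one method preceded the read. A reader trained only afterwards is credited with a method not yet used.

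**3. Never-trained readers.** They have no training date and no method. SAP 7.2 leaves missing values missing, so their reads drop out of both subgroups and have no row of their own.

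**4. Accuracy of exactly 70%.** In lowest terms 70% is 7/10, so the denominator must be a multiple of 10. For n ≤ 15 only n = 10 qualifies, giving 7 of 10. For a 10-image reader:
- at 90% accuracy: P = 120 × 0.9^7 × 0.1^3 = 0.0574, or 5.7%;
- at an assumed 80%: P = 120 × 0.8^7 × 0.2^3 = 0.2013, or 20.1%.

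The next case, 14 of 20, needs a reader with 20 images, hence at least 20 / 0.075 = 266.7, i.e. 267 images in total. With the lowest band at ≤70%, every proportion falls in exactly one band.

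**5. Experience (illustration only).** No reads are affected for a reader who had already read 50 brain PET scans before the first contributed image. At most 15 are affected for one reader at the cap of a 200-image study. Assume true accuracy of 80% below 50 scans and 90% from 50 up, and let f be the misfiled share of the ≥50 row. Row accuracy = 90 − 10f points, and the contrast with 80 is 10 × (1 − f):

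| f | contrast (points) |
|---|---|
| 10% | 9.0 |
| 15% | 8.5 |
| 25% | 7.5 |
| 50% | 5.0 |

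One fully misfiled reader at the cap in a row of 100 reads is f = 15/100 = 15%.

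**6. Boundary symbols.** The SAP prints ≥50 and ≥6 months. Protocol 9.7 prints >50 and >6 months, possibly a symbol lost in text conversion. SAP 8.6.3 shows both ≥ and ≤ correctly around the accuracy bands, so the gap at 70% is clear there whatever happened to the protocol text.

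**The case against.** The strongest reply is that a competent programmer would do the right thing. All training dates are collected, the gap is tied to each image's read date, and a time from training to reading presupposes that training came first. Table templates and the eCRF are separate documents and may settle the rows and the as-of date. The study has no hypothesis and no tests, prospective and retrospective results are reported separately, and nothing shows that any reader trained after a contributed read.

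Much of this stands, and it limits the size of the point. It does not remove it: the written rule says last training, method carries no date, and the SAP should fix the choice before results are seen.

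Several stronger readings are tempting but not supported:
- *The as-of date for experience is wholly undefined.* It is loose. The wording does give one reference point per reader, the study, which fits existing reads badly.
- *Never-trained readers are counted as recently trained.* They are missing under SAP 7.2, not misfiled.
- *Prospective rows are immune.* A reader may retrain after an early prospective read, so they are less exposed but not exempt.
- *The training contrast is necessarily diluted.* Only the experience contrast was modelled. The direction for training depends on which reads move.

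**Conclusion.** The point holds as a minor defect in the written definitions. The training rule is the part that matters: applied literally, it credits a read to training that came later, mainly among existing reads. The gap at 70% is certain on the page but reaches only a result of 7 of 10 for readers with up to 15 images. The experience wording is the least of the three.

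Only secondary descriptive tables are affected. The primary pooled estimates of accuracy, sensitivity, specificity, PPV and NPV do not use these variables. The number of misfiled reads is unknown and may be zero. The 5.7% rests on the plan's 90% and independent reads by a reader with exactly 10 images. The 20.1% and the shrinking contrasts rest on accuracies and shares assumed here, and they illustrate the mechanism without estimating its effect.

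**What to change.** 1. **Training (SAP 7.1 and 8.6.3).** Derive time since training and training method from training completed on or before each read date, and add a row for reads with no training before the read. One reader's reads may then fall in more than one row, so say that the reader is counted in each.
2. **Bands.** Change the lowest band to ≤70% in SAP 8.6.3 and protocol 9.7.
3. **Experience.** Define it as brain PET scans read before the reader's first contributed image, existing or prospective, one value per reader, and note that counts are approximate.
4. **Cut-offs.** Check the symbols in protocol 9.7 and align them with the SAP's ≥50 and ≥6 months.

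The cost is a few lines of SAP text, one small protocol wording change and an as-of date on the eCRF item for the scan count. SAP section 9 reports no change from the protocol's planned analysis and would need an entry for anything changed in the SAP alone. Training dates are already collected. For readers trained by both methods each date must be linked to its method, and the documents do not say whether it is. One experience value per reader leaves reads made after passing 50 scans in the <50 row, which should be stated as a limitation.

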5 SAMPLE SIZE AND POWER

Number of Subjects

This study has no formal hypothesis and no statistical tests will be performed. The endpoints of accuracy, sensitivity, and specificity will be summarised descriptively with point estimates and 95% CIs. Although no formal hypothesis will be tested, the sample size is determined to achieve the desired precision in estimating the primary endpoint of the percentage of subjects whose images are correctly classified as positive or negative (accuracy). Assuming that VIZAMYL™ images from 90% of subjects are read correctly by readers who have taken the VIZAMYL™ training programme, 200 subjects will achieve a 95% CI width of less than 10%.

The endpoints of sensitivity and specificity will also be summarised descriptively. This study aims to characterise reader performance in clinical practice so the number of positive and negative images will not be controlled. However, it is expected that most patients who are referred for a VIZAMYL™ scan will have dementia, and most cases of dementia are Alzheimer's Disease (AD). Since brain amyloid is present in AD, it is expected that the majority of patients in this study will have brain amyloid. It is assumed that the majority blinded interpretation of the expert readers will be SOT-positive for approximately 65% of scans, giving a total of approximately 130 scans for sensitivity, with the remaining 70 scans being SOT-negative and therefore usable for calculating specificity. Assuming a sensitivity of 90% and a specificity of 90%, these sample sizes should give reasonably precise 95% CIs for estimating sensitivity and specificity in this scenario (95% CI width of approximately 15% or less).

Accuracy, sensitivity, and specificity will also be calculated by country where all study images from sites within a given country will be pooled for analysis. No country may contribute more than 25% of the total number of images. Because the number of subjects per country is smaller than the overall number of subjects, the level of precision and the width of the CI will be impacted. Again, since the aim of the study is to characterise reader performance in clinical practice, the exact number of images obtained per country and per site is unknown. [Table 5-1](#) provides examples of 95% CI widths for accuracy assuming a few different sample sizes per country to illustrate the change in precision.

Table 5-1 95% Confidence Interval Width for Different Sample Sizes Assuming 90% Diagnostic Accuracy

Sample Size	Actual 95% CI Width	Lower Confidence Limit	Upper Confidence Limit
30	24.4%	73.5%	97.9%
40	20.9%	76.3%	97.2%
50	18.5%	78.2%	96.7%
60	16.7%	79.5%	96.2%

When calculating sensitivity and specificity per country, precision will again be impacted because the sample size per country will be further divided into SOT-positive and SOT-

negative scans. For example, if a country enrolls 40 subjects and 65% of the scans are SOT-positive ($n = 26$) then the width of the 95% CI for sensitivity would be 26.4% (lower confidence limit = 71.8%) and the width for specificity would be 37% (lower confidence limit = 62.4%).

Accuracy by reader will also be presented in a tabular form, though it may be expected that some institutions will have very few scans per reader.

Number of Clinical Readers

The number of clinical readers (1 to 5 per country) was chosen to allow each European country where VIZAMYL™ is commercially available [REDACTED]
[REDACTED].

Number of Expert Readers

The number of expert readers (5) was chosen based on precedent set in prior clinical studies of VIZAMYL™.

6 ANALYSIS POPULATIONS

6.1 Efficacy subject population

The efficacy subject population will consist of all subjects who have an interpretable image that has an available expert majority image interpretation.

6.2 Efficacy clinical reader population

The efficacy clinical reader population will consist of each clinical reader who has interpreted the images included from his/her institution and has had at least one of their image interpretations classified as TP, TN, FP, or FN through comparison with the SOT (the expert reader majority interpretation).

6.3 Safety population (Safety)

The safety population will consist of all subjects who were enrolled in the study and received a dose of VIZAMYL™.

6.4 Exclusions from analysis sets

Subjects who do not meet the definition of the various populations will be determined prior to database freeze and image unblinding.

7 STATISTICAL CONSIDERATIONS AND ANALYSIS

7.1 Derived Variables

Not applicable

7.2 Handling of missing data and outliers

Missing values will not be substituted by estimated values, but treated as missing in the statistical evaluation. All data from all subjects enrolled and imaged in the study will be included in all listings, plots, summary tables, and statistical analyses when appropriate.

7.2.1 Missing data analysis methods

Not Applicable

8 STATISTICAL METHODS

8.1 General statistical conventions

All statistical procedures will be completed using SAS version 9.3 or higher.

Continuous variables will be summarised using descriptive statistics, including number of subjects in the analysis (n), mean, median, standard deviation (SD), and range (minimum and maximum).

For categorical variables, summaries will include counts of subjects and percentages. Percentages will be rounded to one decimal place. Two-sided 95% exact CI will be provided when relevant.

All subject data, including those derived, will be presented in separate data listings showing individual subject values. Unless otherwise stated, unscheduled visit results will be included in date/time chronological order, within patient listings only. All listings will be sorted by investigational site, patient number, date/time and visit. Patient's gender and age will be stated on each listing. Unless otherwise stated, data listings will be based on the safety population.

8.2 Subject disposition

Subject disposition information will be summarised. The disposition summary table will include the following information.

- Number of subjects enrolled (subjects who have signed the informed consent form)
- Number of prospective images
- Number of retrospective images
- Number of subjects in the safety population
- Number of subjects with VIZAMYL™ images included in the efficacy analysis (efficacy subject population)
- Number of subjects who completed the study
- Number of subjects who discontinued the study
- Reasons for withdrawal

The safety population will be used for calculating the percentages.

In addition, a separate table will be provided to summarise the efficacy clinical reader population, the number of clinical readers participating, and number of clinical readers' image interpretations included in the efficacy analysis. Listings will be provided for subject disposition.

8.3 Protocol deviations

Deviations from the protocol will be described and provided in the form of a listing.

8.4 Demographics and baseline characteristics

8.4.1 Subjects-demographic and baseline characteristics

Continuous demographic variable age will be summarised descriptively, and the following categorical variables will be summarised using counts and percentages. Summaries will be provided for prospective and retrospective images along with pooled results based on the safety population.

- Gender
- Race
- Country

Baseline characteristics

- History of renal/hepatic impairment
- Reason for scan
- Type of medical practice of referring physician (primary, secondary, tertiary)
- Type of anatomic images available, if any (MRI and/or CT)

Listings will be provided for each subject's baseline and demographic characteristics.

8.4.2 Clinical Reader - demographic and baseline characteristics

Continuous demographic variable clinical reader's age will be summarised descriptively, and the following categorical demographic and baseline variables will be summarised using counts and percentages. Summaries will be based on the efficacy clinical reader population.

- Gender
- Race
- Country

Baseline characteristics:

- VIZAMYL™ reading training status
- Number of times training done (1, 2, ≥ 3)
- VIZAMYL™ reading training method (electronic, in-person, or both)
- Training with other amyloid PET imaging agents
- Medical specialty
- Time (month) from last training to the date of image interpretation (<6 months, ≥ 6 months)
- Number of brain PET scans read in clinical practice (<50, ≥ 50)
- Type of medical practice (primary, secondary, tertiary)
- Prior experience (clinical or research) with any amyloid PET imaging agent (including VIZAMYL™)

In addition, the following continuous baseline characteristics will be summarised descriptively:

- Duration (months) from last training to the date of image interpretation
- Years of experience reading PET images
- Number of brain PET scans read in clinical practice
- Years of experience reading PET images

- Number of times training done

Listings will be provided for each clinical reader's demographic and baseline characteristics.

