The efficacy clinical reader population will consist of each clinical reader who has interpreted the images included from his/her institution and has had their image interpretations classified as TP, TN, FP, or FN through comparison with the SOT (the expert reader majority interpretation).

Page 29 of 43

Subject Demographics/Other Baseline Characteristics

A table will be provided with the following information:

- Number of subjects enrolled.
- Number of subjects in the safety population.
- Number of subjects with VIZAMYLTM images included in the efficacy analysis.

GE-067-027 C

Version 7.0 Approved

Demographic information (Table 5 above) will be summarised using descriptive statistics.

Study Treatments

All subjects will have received VIZAMYLTM as part of routine clinical practice. The dose and volume administered will be summarised across all subjects.

Clinical Reader Demographics/Other Baseline Characteristics

A table will be provided with the following information:

- Number of clinical readers participating.
- Number of clinical readers' image interpretations included in the efficacy analysis.

Demographic information (Table 5 above) will be summarised using descriptive statistics. Demographic information will be reported for readers who are randomly chosen to participate as well as the complete pool of potential readers who agreed to participate in addition to readers who decided not to participate where data are available.

Primary Analysis

The primary analysis will be the determination of diagnostic accuracy, sensitivity, specificity, PPV, and NPV across readers based on all evaluable images (at least 200 images) (point estimates and exact 95% CIs).

Secondary Analyses

The numbers and percentages of images for which 5 expert readers agree, 4 expert readers agree, and 3 expert readers agree will be summarised. In addition, results will be analysed by the following variables:

- Country
- Time from training to image interpretation (<6 months, >6 months)
- Specialty of the reader
- Training method(s) used by the clinical reader (in-person, electronic, or both)

- Number of scans read by the clinical reader in practice prior to the study (<50, >50)
- Reader classification certainty (1 to 5)

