9.9 Limitations of the Research Methods

The main limitations of this study are:

- 1. Not all countries and sites can be represented because of restrictions due to approval and manufacturing locations.
- 2. Readers who participate may not be fully representative of the population of readers in clinical practice (e.g., untrained readers may be unwilling to participate, and there may not be a balanced split among clinical readers for subgroups such as training type, specialty, etc. since we are not controlling these factors).

The potential for bias from the first limitation cannot be assessed in this study. The potential for bias from the second limitation will be assessed by reporting demographic data (see Table 5) for readers who are randomly chosen to participate as well as the complete pool of potential readers who agreed to participate in addition to readers who decided not to participate, where data are available.

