8.8 Interim analysis

No formal interim analyses (IA) of the data are planned for this study.

**9 CHANGES TO PLANNED ANALYSIS FROM STUDY
 PROTOCOL**

No change in protocol planned analysis.

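### The SAP plans no summary of readers who agreed or declined, although the protocol names that summary as its check on reader-selection bias, and SAP section 9 declares no change

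*SAP*

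**What the plan says.** **Protocol.** Section 9.9 lists unrepresentative readers as the second main limitation, giving the example that "untrained readers may be unwilling to participate". It continues: "The potential for bias from the second limitation will be assessed by reporting demographic data", and names three groups: readers chosen to take part, the pool who agreed, and those who declined. Section 9.7 repeats the commitment under clinical reader demographics, covering "the complete pool of potential readers who agreed to participate in addition to readers who decided not to participate where data are available". Section 9.3.1 provides for the data: "every effort will be made to collect these data from readers who decline to participate as well".

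**SAP.** Section 8.4.2, on clinical reader demographics and baseline characteristics, states: "Summaries will be based on the efficacy clinical reader population". Section 6.2 defines that population as readers who interpreted the included images from their institution, each of whom "has had at least one of their image interpretations classified as TP, TN, FP, or FN". The only other reader table is in section 8.2: "a separate table will be provided to summarise the efficacy clinical reader population, the number of clinical readers participating", plus the number of interpretations analysed. Section 9, on changes from the protocol, reads: "No change in protocol planned analysis".

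**Accuracy bands.** Protocol 9.7 and SAP 8.6.3 both print a band below 70% followed by a band above 70% up to 80%, with no band containing 70% itself.

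**The concern.** The research question is how effective reader training is in practice, and both documents allow clinical readers with or without that training. If untrained readers tend to decline, the pooled accuracy describes a better-trained group than the one that reads these scans routinely. Protocol 9.9 recognises this and offers one check. It says bias from its first limitation, unrepresented countries and sites, cannot be assessed, so the reader comparison is the only bias assessment offered for the listed limitations.

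An analyst who follows the SAP exactly will not produce that check and will have no prompt to report its absence. Protocol 9.7 requires departures from its planned analysis to be explained in the final report, whereas SAP section 1 asks only for departures from the SAP to be justified.

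**Working it through.** The main point is a comparison of texts. The arithmetic only gives scale.

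**1. Which readers each document covers**

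| Reader group | Protocol 9.7 and 9.9 | SAP 8.4.2 with 6.2 |
|---|---|---|
| Participating, with a classified read | reported | summarised |
| Agreed, but no classified read | reported within the agreed pool | excluded by definition |
| Declined | reported where data exist | excluded by definition |

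SAP 8.2 adds counts for participating readers only. SAP 8.4.2 also plans listings for each clinical reader, but does not say these include decliners, and a listing is not a summary comparison. No other SAP section mentions either missing group.

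**2. Variables.** Protocol Table 5 has 14 rows for clinical readers. SAP 8.4.2 covers 13 of them, counting training dates through time since last training; institution is absent. For the agreed pool and the decliners it covers 0 of 14.

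**3. How fine the comparison could be.** Protocol 9.2.5 caps a reader at 7.5% of images. Since 13 × 7.5% = 97.5% < 100%, at least 14 readers are needed. With the minimum of 14, one reader is 1/14 = 7.1 percentage points of any participant percentage, such as the share trained. The comparison would be descriptive only.

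**4. Minor: the gap at 70%.**
- At 200 images the cap is 0.075 × 200 = 15 images per reader. Of all k-of-n results with n ≤ 15, only 7/10 falls in no band.
- The next case, 14/20, needs a cap of 20 images: 0.075 × 266 = 19.95 is too few and 0.075 × 267 = 20.025 is enough, so the total must reach 267.
- Take a reader with exactly 10 images and an assumed true accuracy of 90%, the planning value. P(X = 7) = 120 × 0.9⁷ × 0.1³ = 0.057. At an assumed 80% it is 0.201.
- With 20 images and 90%, P(X = 14) = 0.009.
- The documents give no per-reader image counts, so these probabilities are conditional illustrations.

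**5. Minor: wording.**
- Protocol 9.7 says the bands count clinical readers. SAP 8.6.3 does not state the unit.
- Protocol 9.7 and 9.9 describe participating readers as chosen at random. Section 9.2.5 takes in eligible, willing readers and 9.4.1 says readers will be selected, both at 1 to 5 per country. Neither describes a random step.

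**The case against.** The strongest reply is that the protocol promise is conditional and the SAP does not revoke it. Decliner data are to be reported only where available, and their collection is best effort. The no-change statement could be read as leaving protocol 9.7 in force, and the table templates are in a separate document not available here. If every eligible, willing reader is included, the agreed pool nearly coincides with the participants, so the real loss is one group, the decliners. The primary estimate is untouched.

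Much of this is fair, and it limits the point. The finding concerns the SAP text, not what the templates may contain. The agreed-pool column may add little, and the decliner column may be thin. But availability of data governs how full the column is, not whether a table is planned. SAP 8.4.2 is also not merely silent: it names a population that shuts these groups out.

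On the minor items, the protocol's band symbol may have been lost in conversion, since it also prints strict inequalities at 6 months where the SAP has ≥. That explanation is weaker for SAP 8.6.3, where ≥ and ≤ survive nearby. The missing unit is a small wording matter, because the preceding SAP sentence counts readers. The random-choice wording may reflect a selection step that is simply not described.

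**Conclusion.** The concern holds. Following the SAP as written omits the protocol's stated check on reader-selection bias, and the no-change declaration in SAP section 9 is incorrect on this point. Three groups were committed to and one is planned.

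The consequence is for interpretation. The missing table would show whether participants differ from non-participants, notably in training status, but would not measure bias. No effect on accuracy can be calculated from the documents and none is claimed. The conclusion rests on the SAP text alone and assumes that the unseen templates do not supply the missing columns. It should be corrected, but it does not threaten the primary analysis. The 70% gap and the wording points affect secondary descriptive tables and text only.

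**What to change.** **Main change.** Add to SAP 8.4.2 one descriptive table, without tests, of the Table 5 reader variables. Use columns for participating readers, all who agreed, and decliners where data exist. Also give the numbers contacted, agreed, declined, and declined without data. These counts go slightly beyond the protocol's promise, but without them a sparse decliner column cannot be interpreted. Do not compare time since training across columns unless all use the same reference date. If the table will not be produced, state this with a reason in SAP section 9.

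**Minor changes.**
- Check the protocol's original symbol, then close the band at 70% in the same direction in both documents. The direction matters little: for a reader with 10 images and true accuracy 90%, the lowest band has probability 7.0% if it includes 70% and 1.3% if it does not.
- State in SAP 8.6.3 that the bands count clinical readers.
- Reconcile the random-choice wording in protocol 9.7 and 9.9 with 9.2.5 and 9.4.1, either by describing how readers are selected or by removing the phrase.

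**Cost.** One extra table from data the protocol already intends to collect, plus SAP wording. No planned table is lost. The protocol edits can wait for its next update. The drawbacks are a possibly sparse decliner column and an agreed-pool column that may largely repeat the participants.
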